7.7 Early Termination Visits

Whenever possible, subjects who withdraw early or who are asked by the investigator to cease participation in the study will have one final visit to collect study medication and to follow up regarding adverse events.

8 Study Evaluations and Measurements

The following measures will be collected during all outcome assessments, unless otherwise specified.

8.1 Primary Outcome Measure: Body Weight

Body weight will be measured at screening and at all clinic visits. However, for purposes of the primary outcome, weight will be assessed during outcome assessments at baseline (at the start of the BT run-in); at randomization (week 0); and at week 24. Weight will be measured on a digital scale (to the nearest 0.1 kg) with subjects dressed in light clothing, without shoes. Two measurements will be taken on each occasion.

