5.2 BT Intervention

Following randomization, all subjects will continue to attend individual (20-30 minute) BT sessions weekly for 12 weeks, then every other week until week 24 (total of 18 sessions). Subjects will be instructed to continue to follow their calorie goal and to engage in low-to-moderate intensity physical activity (e.g., walking), gradually building to a goal of ≥ 180 minutes per week (spread across 5 days) by week 24. They will be provided a curriculum on behavioral weight control, based on prior studies,^{80, 81} that includes self-monitoring, stimulus control, goal-setting, problem-solving, cognitive restructuring, and relapse prevention. Subjects will continue to monitor their food intake, physical activity, and weight online (e.g., Myfitnesspal) unless they prefer paper diaries. Subjects who miss a treatment visit will be contacted by the research coordinator and invited to complete a make-up session with study staff.

Initially, BT sessions were primarily provided in-person (make-up sessions were conducted in person or by phone). Consistent with University policy, all BT sessions will be provided by telehealth (phone or secure teleconferencing system) while recommendations to maintain remote activities due to COVID-19 remain in place.

BT interventionists will include RDs, NPs, and psychologists who are experienced in delivering lifestyle modification. Before beginning the study, interventionists will receive a 2-hour overview of obesity and its behavioral management, followed by ongoing weekly group clinical supervision. The PI will observe each provider delivering a treatment session at least once every 6 months to provide individualized feedback and ensure protocol adherence.

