9.1 Sample Size and Power Determination

A total sample size of 150 subjects will provide at least 80% power to detect all three primary outcomes. All power analyses were conducted using G*Power 3.1 at an alpha of .05. A correction for multiple comparisons is not proposed due to the preliminary nature of this research.

Phase 1: For the co-primary outcome - percent weight loss at the end of the BT run-in as predicted by baseline satiety, postprandial GLP-1, and gastric emptying - an estimated effect size for each predictor of

$\rho^2 = .042$ was selected as the lower estimate from studies predicting weight loss from VAS satiety ratings and GLP-1 (ρ 's $\geq .20$).^{16, 106} (We did not find studies using gastric emptying to predict weight loss, and the effect sizes for comparisons between BMI categories of $\rho^2 = .07 - .30$ were less conservative.^{43, 78}) Based on this estimate, a sample size of 150 subjects would yield 80% power to detect statistical significance for the three individual predictor variables. The second co-primary outcome - non-responder status as predicted by these three predictors in discriminant analysis - would have 90.1% power with this sample size, based on power analysis for a 2-group MANOVA for 3 response variables^{107, 108} with an estimated combined effect size of $\rho^2 = .10$.

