Phase 2: For the primary outcome - percent weight change from randomization to week 24 among early non-responders - estimated group means, variances, and attrition rates were derived from data from prior studies conducted at our Center and from previous research in early non-response to BT e.g.,⁴. The estimated treatment effect is based on the placebo-subtracted effect of 28 weeks of phentermine 15.0 mg of 4.5 kg (4.4% of initial weight), as determined by a multi-arm RCT that enrolled 219 total patients in the placebo and phentermine 15.0 mg groups.⁷⁷ We selected this result as the basis of our power analysis because it most closely matched the phentermine dose and duration used in the present study. Other previous RCTs examining the effect of phentermine monotherapy have typically administered a 30.0 mg dose for 12 to 16 weeks. The majority of these trials have achieved larger placebo-subtracted weight losses of 5.4 to 7.8 kg.^{72, 74-76} (One randomized trial reported a 4.0 kg placebo-subtracted loss with a different formulation, phentermine resin 30.0 mg,⁷³ and one reported a 3.3% placebo-subtracted loss when both phentermine 37.5 mg and placebo were combined with a 900-1100 kcal/day meal replacement diet, resulting in large mean weight losses in both groups.¹⁰⁹) An additional study suggested that the difference in mean weight loss between phentermine 15.0 mg and phentermine 30.0 mg (both when combined with lorcaserin) is small (0.6 kg mean difference).¹¹⁰ We therefore believe that participants provided with 24 weeks of phentermine 15.0 mg are likely to achieve a placebo subtracted loss of $\geq 4.5\%$ of initial weight. (Most early phentermine studies reported results in kg, which is roughly equivalent to percent weight loss in populations with obesity.)

We predict a 24-week post-randomization weight loss among early non-responders of 6.5% in BT+M and 2.0% in BT+P, with expected standard deviations of 5.5%. We expect 33% of the initial baseline sample of 150 subjects to be categorized as early non-responders following the BT run-in.^{4, 7, 8} Based on these estimates, a randomized sample size of 50 non-responders (25 per group), assuming a 20% attrition rate, will give us 81.5% power to detect between-treatment group differences at week 24 of 4.5% (effect size: $d = 0.82$).

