9.2 Statistical Methods

Data quality and integrity will be checked by assessing the data for missing and out-of-range values and univariate normality with basic statistical procedures, including descriptive statistics and visual graphical displays (e.g., histograms, scatter plots). All questions of data quality and integrity will be investigated before any statistical modeling is conducted. To test the adequacy of randomization, preliminary analyses will include a comparison of demographic and baseline characteristics between randomized treatment groups (BT+P and BT+M; t-tests or Wilcoxon rank sum tests for continuous variables and Chi-Square test or Fisher's Exact test for categorical data). If baseline imbalances are observed, the relevant variables will be included as covariates in analyses relevant to those outcomes.

All analyses will be conducted using the ITT principle. Analyses will be two-tailed with an alpha of 0.05, and will be conducted using SPSS version 24.0 or SAS version 9.4. For all analyses, residual analyses will be conducted to check for outliers, influential points, and violations in the normality assumption. If violations are detected, variance-stabilizing transformations will be considered.

Phase 1: Analyses will be based on the initial population of subjects who attend at least one post-baseline treatment visit during the BT run-in. Multiple regression will be used to evaluate predictors of early weight loss with BT (% loss at week 0) and discriminant analysis will be used to assess which variables predict categorization as a non-responder (who has lost $< 2\%$ of initial weight at week 0). The primary analyses will test the hypothesis that the set of baseline satiety measures (VAS satiety ratings, postprandial changes in GLP-1, and gastric emptying) predict these outcomes when considered simultaneously. Additional analyses will evaluate demographic characteristics, secondary predictor variables (fasting hunger, RRV_{food}, reinforcing efficacy of food, impulsivity, fasting ghrelin, fasting leptin, and lower postprandial changes in insulin and PYY), and exploratory variables as predictors of early weight loss.

Factor analysis will be used to assess whether predictor variables cluster into phenotypes.

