All analyses will be conducted using the ITT principle, in which all available data on all randomized patients are included. This approach minimizes bias if subjects drop out of the intervention for different reasons. Assuming adequate fit of the mixed effects models to the data, the proposed nested random effects models are the most robust to missing data assumptions among standard longitudinal models that analyze all subjects regardless of how many post-randomization visits are missed.¹¹¹ The following missing or unbalanced data scenarios can be accommodated by such models: attrition (drop out), missed interim visits, and missing covariate data where a subject is interviewed but data are missing on covariates of interest. All three types of missing data are handled by way of maximum likelihood under the proposed mixed effects models and the missing at random assumption (MAR). Therefore, we will explore the potential bias of missing data by comparing completers and non-completers to see if they differ systematically on values of non-missing variables. There are many ways to assess the assumption of MAR. We will consider imputing missing endpoint data using multiple imputation techniques, fitting selection models (e.g. MNAR), and fitting pattern mixture models. Sensitivity analyses, including an analysis of the protocol-compliant population, also will be conducted.

Participants' data will be excluded from analyses in the event of pregnancy, amputation, bariatric surgery, or death. Any data collected following such events will be treated as missing, using the analytic methods described above. Additional criteria associated with subject censorship will be considered prior to initiating recruitment.

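### Section 8.1 keeps interim weights out of the primary outcome while section 9.2 relies on them for missing data, and telehealth removes the BT-session weights that could close the gap

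*Combined protocol and SAP*

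**What the plan says.** - **Weighing (8.1).** "Body weight will be measured at screening and at all clinic visits". The next sentence narrows this. For the primary outcome, the weights are those from the outcome assessments at baseline, week 0 and week 24.
- **Treatment format (5.2, 7.4).** After randomization there are 12 weekly and 6 every-other-week sessions. While COVID-19 recommendations last, "all BT sessions will be provided by telehealth (phone or secure teleconferencing system"). Subjects log their own weight online or on paper; no analysis is said to use it.
- **Primary model (9.2).** A mixed model with group and time (week). The weeks are not listed.
- **Missing data (9.2.1).** "All analyses will be conducted using the ITT principle, in which all available data on all randomized patients are included". Dropout and missed interim visits are said to be handled by maximum likelihood under missing at random (MAR). Multiple imputation, selection models and pattern mixture models are to be considered.
- **Other contacts.** Monitoring visits at weeks 2 and 4, and vital signs at in-person visits in listed weeks (10.6); six dispensing occasions (5.3); medication-distribution visits excepted from phone make-up (7.5); a final visit where possible (7.7, weight not named).
- **Endpoint follow-up (7.5).** Everyone who completes a randomization visit is invited to week 24, even after stopping medication or BT.

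**The concern.** A mixed model protects against dropout under MAR only through outcomes seen before the subject left. Percent change from randomization is zero at week 0 by construction. A subject whose only post-run-in weight is at week 0 therefore tells the model essentially nothing about week 24, and for such subjects the likelihood analysis amounts to a completer analysis.

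Section 9.2.1 writes as though interim weights are in the model; section 8.1 reads as though they are not. Telehealth adds a second difficulty. Even if the team intends to use clinic weights from treatment visits, those from BT sessions are not taken while sessions are remote, and the text gives no remote weighing procedure. Section 10.6 adapts vital signs to whichever visits are in person, but section 8.1 has no matching provision.

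At stake are the precision of the week 24 contrast in a trial of about 50 subjects and, if dropout is driven by early weight loss differently in the two arms, its accuracy.

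**Working it through.** **1. The plan's power figure.** Inputs from 9.1: "We predict a 24-week post-randomization weight loss among early non-responders of 6.5% in BT+M and 2.0% in BT+P", "with expected standard deviations of 5.5" percent, and "a randomized sample size of 50 non-responders (25 per group), assuming a 20% attrition rate, will give us 81.5% power". So d = 4.5/5.5 = 0.818, and 25 × 0.8 = 20 completers per arm. Section 9.1 gives alpha without sidedness ("All power analyses were conducted using G*Power 3.1 at an alpha of .05"); section 9.2 says "Analyses will be two-tailed with an alpha of 0.05". Power of a two-sample t-test (noncentral t):

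| Case | Power |
|---|---|
| One-sided, 20 per arm | 81.5% |
| Two-sided, 25 per arm, no attrition | 80.9% |
| Two-sided, 20 per arm | 71.3% |

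The stated 81.5% matches the first row and nearly the second. The plan as written is the third, so 71.3% is the reference here. That discrepancy is a separate point.

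**2. Which weights exist after week 0.**

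| Reading | In-person period | Telehealth period |
|---|---|---|
| 8.1 taken strictly | week 24 only | week 24 only |
| All clinic weights enter the model | up to 12 + 6 = 18 session weights, other clinic visits, week 24 | no session weights; any in-person monitoring, dispensing or final visit; week 24 |

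On the strict reading, anyone missing week 24 has no post-randomization weight in the analysis, whatever the period. On the wider reading the gap is mainly a telehealth one, of unknown size.

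**3. Precision.** Suppose all 25 per arm have one interim weight with correlation ρ to week 24, and 20 have week 24. The likelihood estimate of an arm's week 24 mean has variance 5.5² × v, with v = (1 − ρ²)/20 + ρ²/25, and effective n = 1/v. The values of ρ are assumed.

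| ρ | v | Effective n per arm | Two-sided power |
|---|---|---|---|
| no interim weight | 0.0500 | 20.0 | 71.3% |
| 0.5 | 0.0475 | 21.1 | 73.6% |
| 0.7 | 0.0451 | 22.2 | 75.9% |
| 0.9 | 0.0419 | 23.9 | 79.0% |

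**4. Bias.** Let z be standardized interim loss. Assume drug-arm dropout is random at 20%, and placebo dropout follows logit P = a − s·z with a set to give 20%. The mean of z among placebo subjects who stay is then m = 0.096, 0.173 and 0.227 for s = 0.5, 1.0 and 1.5. The placebo completer mean is too high by 5.5 × ρ × m, and the difference is too small by the same amount:

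| s | ρ = 0.5 | ρ = 0.7 | ρ = 0.9 |
|---|---|---|---|
| 0.5 | 0.26 | 0.37 | 0.48 |
| 1.0 | 0.48 | 0.67 | 0.86 |
| 1.5 | 0.62 | 0.87 | 1.12 |

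The completer difference is therefore 4.5 − 0.26 = 4.24 down to 4.5 − 1.12 = 3.38. Two contrasts:

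- **Same mechanism in both arms.** The shifts cancel and the completer estimate stays at about 4.5.
- **Opposite directions (s = 1 on placebo, −0.5 on drug).** The shift is 5.5 × ρ × (0.173 + 0.096), giving 3.8 at ρ = 0.5 and 3.2 at ρ = 0.9.

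A model that includes the interim weight returns about 4.5 in every case. This follows from the set-up, in which dropout depends only on a weight seen for everyone.

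**The case against.** A reader might infer that telehealth by itself turns the intention-to-treat model into a completer analysis, that telehealth-era dropouts have no post-randomization weight at all, and that the strength of the missing-data protection is fixed by calendar date. The documents do not support this.

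- Section 8.1 keeps treatment-visit weights out of the primary outcome in both periods, so telehealth is not the sole cause. Its effect depends on interim weights entering the model, which 9.2 implies but never states.
- The loss of all 18 weights applies to BT sessions only. Monitoring, dispensing and final visits may yield clinic weights. How many were in person is not stated.
- The in-person period did not guarantee 18 weights either. Section 5.2 describes its sessions as mostly in person, with some make-ups by phone.
- The body of Table 1 (section 6) could not be read in the copy available, so a weight schedule there cannot be excluded.
- Leaving treatment is not the same as missing week 24 (7.5), and 9.2.1 plans a comparison of completers with non-completers plus sensitivity analyses.
- The bias range rests on assumed correlations, dropout slopes and a one-arm mechanism, none of them from the documents. Subjects who leave before any interim weight would not be recovered.

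All of this stands, and it limits the claim. It does not reconcile 8.1 with 9.2 or supply a remote weighing procedure. The imputation models in 9.2.1 are only to be considered, and would have little to draw on without interim weights.

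**Conclusion.** The concern holds as a conflict between 8.1 and 9.2, made worse by telehealth. If only weeks 0 and 24 enter the model, the missing-data protection described in 9.2.1 is essentially absent for anyone who misses week 24.

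The precision loss does not need differential dropout. Two-sided power is 71.3%, where one interim weight on every dropout would give 73.6% to 79.0% at assumed correlations of 0.5 to 0.9.

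The bias is conditional: 0.3 to 1.1 points of the 4.5 if placebo dropout alone follows poor early loss and all subjects are affected, shrinking roughly in proportion to the share affected. It is nil if dropout works alike in both arms, somewhat larger if the arms run in opposite directions, and could take the other sign under other patterns. Treat the range as an illustration, not an estimate. The point merits a change because the change is cheap, with medium confidence while the number of in-person visits during telehealth and the content of Table 1 are unknown.

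**What to change.** 1. **8.1 and 9.2.** State that all available post-randomization clinic weights enter the mixed model, list the weeks, and keep week 24 as the tested time point.
2. **8.1.** At each telehealth session, record the subject's self-monitored weight with a source flag (home or clinic).
3. **9.2.1.** Commit to a multiple-imputation sensitivity analysis of missing week 24 weight that uses home weights only as auxiliary variables, each as change from the subject's own first home weight. Report the week 24 difference with and without them.
4. **Reporting.** Give, by arm and by period (in-person or telehealth), the number of subjects with no post-randomization weight.

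Cost: a short amendment and one added field per session. Home weights are noisier than clinic weights and end when session attendance ends, so they cannot help with subjects who leave at once and do not replace clinic weights for the endpoint.

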8.2 Phase 1 Predictor Variables

8.2.1 Appetite, Neuropeptides, and Gastric Emptying

During the two-hour in-person outcome assessment at baseline (week -5), randomization (week 0) and week 24, subjects will first complete measures of appetite, neuropeptides, and gastric emptying before and for 60 minutes after consumption of a liquid test meal (e.g., Muscle Milk). The test meal size (oz and kcal) will vary by sex with women consuming 70% of the amount provided to men. Subjects will be asked to fast for 8 hours prior to the in-person assessment (overnight fast), and research staff will confirm the timing of the subject's last ingestion prior to beginning the assessment.

Appetite measures are perceived ratings of hunger, fullness, and satiety that reflect both objective (e.g., physiological) and subjective (e.g., learned) components of appetite. They will be assessed using 100-mm visual analog scales (VAS) with opposing anchors (e.g., "extremely full" to "not at all full").^{16, 17} The satiety quotient (SQ) will be the primary measure of perceived satiety and reflects the extent to which the liquid test meal reduces appetite sensations per unit of intake (e.g., kcal),^{16, 17} calculated as: SQ (mm/kcal) = [(fasting rating before preload – 60 min post-preload rating)] / (energy content of preload) x 100. Physiological appetitive response will be measured as: 1) fasting levels of circulating neuropeptides associated with appetite (GLP-1, insulin, PYY, leptin, and ghrelin); 2) postprandial changes in these neuropeptides, calculated as the 60-minute area under the curve (AUC);⁴⁵ and 3) gastric emptying as assessed by an acetaminophen test (60-minute AUC).⁸⁷⁻⁸⁹ Because acetaminophen is minimally absorbed by the stomach but quickly enters the bloodstream in the small intestine, gastric emptying is considered to be the primary factor influencing its appearance in the blood.⁸⁷⁻⁸⁹ Maximum blood concentration of acetaminophen is reached in 30 to 60 minutes; therefore, the 60-minute AUC is thought to represent rapidity of gastric emptying.⁸⁹

Blood samples and VAS scales will first be completed in a fasted state. Subjects will be given 1.5g of acetaminophen with 50 ml of water.⁸⁷⁻⁸⁹ They will then be asked to consume a liquid test meal within a 10-minute period. Subjects will repeat VAS ratings at 10-minute intervals after consumption of the test meal.²⁷ Postprandial blood samples will be collected at 30- and 60-minutes post-ingestion to evaluate changes in circulating neuropeptides and acetaminophen absorption. Protease inhibitors and DPP4 inhibitors will be added to samples to be assayed for GLP-1, PYY, and ghrelin to prevent enzymatic breakdown. Samples will be centrifuged at 4°C, separated, and frozen at -80°C for later analysis.

8.2.2 Impulsivity

After completion of the final blood draw and appetite ratings, subjects will complete measures of impulsivity (delay discounting; DD), reinforcing efficacy (questionnaire), and the relative reinforcing value of food (RRV_{food}; baseline [week -5] only). The completion of these tasks following consumption of the liquid meal is designed to reduce the effect of hunger on food reinforcement.^{e.g., 33}

DD is conceptualized as an aspect of impulsivity that reflects difficulty with inhibiting responses to rewarding stimuli. The measure indicates the degree to which delaying an outcome reduces its perceived value. DD will be assessed via a computer program in which subjects are offered choices between small, immediate rewards and larger, delayed rewards.^{e.g., 28, 32} The size of the larger amount is fixed, while the size of the smaller reward and length of delay vary between trials. Indifference points are calculated as the point at which the subject switches preference from the immediate to the delayed reward, and the AUC (representing the ratio of immediate reward size to time delay) will be used as the primary outcome.^{28, 32}

8.2.3 Relative Reinforcing Value of Food

RRV_{food} refers to how hard a person is willing to work to gain access to a food reinforcer. Subjects are allowed to work to earn points from a slot machine task at either of two computer stations, one of which

provides points towards obtaining a preferred high-calorie food, and the other points towards a preferred low-calorie food. e.g., 29, 30 Points are earned on a progressive ratio scale that increases at fixed intervals. The primary outcome is the number of food reinforcer points earned, which is thought to reflect the subject's willingness to allocate time and effort to obtaining desired foods.

